# **Concomitant Medications:**

During the study treatment period, the following medications are prohibited:

- Initiation of any antidiabetic agents, including oral or injectable antihyperglycemic agents
- Systemic use of glucocorticoids for more than 10 consecutive days.
- Initiation of any weight loss drugs
- For patients in both groups, background metformin should be maintained throughout the study unless down-titration is required for safety reasons.

# **Assessment of Results:**

The primary outcome of *treatment adherence* with the use of Insulclock with feedback or no feedback information (blinded) will be determined by the percentage of patients and number of insulin omission, mistiming and dosing. Number insulin irregularities will be registered on the Insulclock device and data will be retrieved during each clinic visit.

**For treatment satisfaction**, subjects' responses to questions 1, 7 and 8 of the DTSQc will be used. A comparison of the score on the DTSQs from week 12 to week 24 as well as using the score on the other questions of the DTSQc, which would overcome the ceiling limitation of using the DTSQs by itself, will also be used to assess treatment satisfaction . The Diabetes Treatment Satisfaction Questionnaire Status (DTSQs) form will be administered at weeks 0, 12 and 24.

Questionnaires will be given at week 0 for standardization purposes. The amplitude of the score on the DTSQc gives the degree of change in satisfaction while the direction (positive or negative) will provide guidance on the preference of one device over the other (i.e., if we predict that patients greatly prefer alarm reminders over nothing and he/she started the group 1 with daily reminders then transitioned to group 2 without the daily reminders, his/her score would be '-3', whereas if he/she was initially not getting the daily reminders followed by the daily reminders then the score would be '+3').

**Ouality of life** will be assessed at baseline and again at weeks 12 and 24 in order to determine the impact of the type of therapy on this outcome. Patients will be given the Diabetes Quality of Life Clinical Trial Questionnaire-Revised (DQLCTQ-R), the Problem Areas In Diabetes scale (PAID) and the Elderly Diabetes Burden Scale (EDBS) at baseline, weeks 12 and 24 to assess their quality of life and any potential impact of the treatment regimen .

*Glycemic Control* will be assessed via HbA1c at weeks -1, 12 and 24 and via fasting blood glucose averages at weeks 0, 12 and 24 from point of care testing during the preceding week.

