# Aim 2. To determine whether the Insulclock system yields higher treatment satisfaction scores in poorly controlled patients with T2D compared to a conventional insulin pen device.

Aim 3. To explore whether changes in adherence with the Insulclock system results in improved glycemic control, as measure by change in HbA1c from baseline, when compared to conventional insulin pen device.

Study Rationale. Poor adherence to medical treatment is common and is associated with increased risk of morbidity in patients with diabetes. Insulin non-adherence has been reported in up to two-thirds of patients, with approximately one-third reporting an average of three episodes of insulin omission/nonadherence within the previous month. Regimen complexity, in terms of the number of the treatments and frequency of administration, is known to have a negative impact on adherence. Patients with irregular mealtime and active social-work schedule were more likely to have insulin irregularities, many of them intentional omissions. In patients with T1D, poor adherence is the main cause of hyperglycemic crises accounting for more than half of admissions with hyperglycemic crises. Several devices have been designed to improve insulin adherence including new delivery options like smart pens with memory functions and electronic display; however they have significant limitations and their efficacy in improving treatment adherence or in improving glycemic control have not been tested in rigorous randomized clinical trials. The Insulclock device allows to record date, time, dose of the last injection, as well as type of insulin used, and remaining insulin volume in the pen device. A major advance of Insulclock over available smart pens is its ability to send visual and acoustic alert message directly from the device or via text to patients and caretakers in the event of insulin omissions and mistiming. In addition, the large volume data storage will allow patients and healthcare providers to download information on insulin patterns and omissions over a long period, allowing for a better understanding of insulin adherence. The present study will test whether the Insulclock improves adherence, quality of life, treatment satisfaction, and glycemic control compared to the standard pen device.

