### **Study Visits**

Screening (Visit 1)

Approximately 1-2 weeks prior to the start of the study, all potential study patients will be screened to check their eligibility after signing the informed consent form (ICF) and assigned a patient identification number. Medical history, physical examination, height, weight, vital signs, pre-existing conditions, and concomitant medications will be recorded during this visit. Laboratory assessments performed at Visit 1 to determine eligibility for the study include pregnancy tests for females, and HbA1c, serum chemistry, assays. Patients who do not meet all the inclusion criteria at Visit 1 will be considered screen failures and will not be randomized to participate in the study.

Eligible patients will be trained on the use of the glucometer to monitor their BG levels. Patients will be given diabetes diaries and associated training to record all glucose levels, insulin doses, and episodes of hypoglycemia.

Insulin administration technique will be reviewed prior to randomization to ensure good technique. Reinforcement will be provided as needed during the follow-up visits.

Only eligible patients treated with a once daily insulin dose of NPH, detemir, glargine insulin will be switched to SoloSTAR pen (glargine U100) at a total dose (TDD).

Antidiabetic agents will be continued at the same dose, except insulin secretagogues which can be stopped if HbA1c is <8% or reduced by half if HbA1c is >8%.

Patients will be instructed in performing glucose testing at home before meals, with a minimum of 2 out of the 4 pre-meal and bedtime glucose measurements per day. In addition, patients must perform a 7-point SMBG (fasting, before meals, 2 hours after meals, and bedtime) done between 3 to 5 days prior to Visit 2.

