One week after screening and before randomization, eligible participants will receive an Insulclock device. They will be properly trained on how to use it, charge and connect Insulclock to their mobile devices. Insulcloud will make smartphone available for subjects, who do not own a smartphone, during the course of the study. Technique skills such as the ability to navigate the app, press the button for 5 seconds while giving insulin injection, and how to connect the device to their phones will be explained. They will be asked to use the Insulclock with their insulin pen, to get familiarized with it. An assessment will be done after the week of using the device in order to review quality and understanding of the technology. Those subjects that fail to use the device properly will be deemed Screen Failures.

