### Analysis of Primary Endpoint:

The primary outcome of treatment adherence with the use of Insulclock with feedback or no information (blinded) is whether a patient has a good adherent to the treatment regimen (assessed based on insulin omission, mistiming, and dosing). Given the 2 by 2 cross-over design, the superiority of the Insulclock system over the conventional insulin pen device will be determined by comparing the percent of patients showing a good treatment adherence with Insulclock but a poor treatment adherence with the conventional device to the percent of patients showing a poor treatment adherence with Insulclock but a good treatment adherence with the conventional device. We will perform this comparison based on McNemar's test assuming the period effect is negligible. We will further conduct logistic regression to accommodate potential period effect and adjust for other potential confounders. We will apply standard model selection and model checking procedures (such as the Hosmer-Lemeshow tests) to decide and evaluate the final model. A p value of <0.05 will be considered significant.

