### **Power Considerations**

This is a pilot study and we plan to recruit 40 subjects for each study group. Our power calculation is mainly based on the binary primary outcome. We assume no more than 15% attrition rate, and assume no period

effect. In the following table, we give the power for detecting the superiority of Insulclock based on Exact Test for Binomial proportion with alpha=0.05, under different projections for the proportion of subjects showing treatment preference (i.e. adherent under one treatment but not under the other), denoted by Ptp, and projections for the probability of preference to Insulclock given showing treatment preference, denoted by p.

	P tp					
Power		90%	80%	70%	60%	50%
р	0.6	31.2%	28.2%	21.5%	17.8%	13.9%
	0.7	87.9%	83.7%	74.9%	66.5%	55.4%
	0.8	>99%	>99%	>99%	97.6%	93.8%
	0.9	>99%	>99%	>99%	>99%	>99%

Regarding the secondary outcomes, the power calculations can be made conservatively based on superiority hypotheses without specifying the equivalent margins. For continuous secondary outcomes, we would have over 80% power to detect outcome difference of 0.41 times the standard deviation based on paired t tests, with alpha=0.05, assuming equal outcome standard deviations for Insulclock and the conventional device, and within subject correlation equal to 0.3.

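### Adherence is counted from the device record alone, with no rule for unlogged injections; if these are commoner without alerts, the primary comparison is biased toward feedback

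*Combined protocol and SAP*

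**What the plan says.** Assessment of Results names the device as the source of the primary count: "Number insulin irregularities will be registered on the Insulclock device and data will be retrieved during each clinic visit". Analysis of Primary Endpoint reduces this to a yes/no outcome per patient and period, "whether a patient has a good adherent to the treatment regimen (assessed based on insulin omission, mistiming, and dosing"), and tests it within patient: "We will perform this comparison based on McNemar's test assuming the period effect is negligible". Neither section defines an omission, sets the cut-off for good adherence, or says how to classify a day without a device record.

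Under Methods, both conditions use the device, but only one gets daily smartphone information and reminders about missed doses.

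Study Visits shows that the device needs upkeep by the patient: "They will be properly trained on how to use it, charge and connect Insulclock to their mobile devices". The same section requires a week of practice before randomization and treats those who cannot use the device properly as screen failures. It also creates a second record of injections: "Patients will be given diabetes diaries and associated training to record all glucose levels, insulin doses, and episodes of hypoglycemia". The diaries are reviewed for insulin self-administration at clinic visits. Study Rationale says the device also records "remaining insulin volume in the pen device". No section uses the diary or the pen volume to check the device count.

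**The concern.** The randomized intervention can act on the measuring instrument. An injection given with the device detached or not working leaves no record. In the feedback condition, a reminder or a gap in the daily information can show the patient that the device is not logging. In the other condition nothing does, and the fault may last until a clinic visit. With telephone visits at two-week intervals in between, office visits 2, 5 and 8 are about six weeks apart.

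If unlogged injections are therefore more frequent without alerts, patients with identical injection behaviour will look less adherent in that condition. The crossover does not cancel this, because the error follows the condition and not the patient. The planned logistic regression adjusts for period and confounders, which does not address it either. At stake is whether a significant primary result means fewer missed injections or only fewer missed logs.

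**Working it through.** **1. The plan's own power figures.** Power Considerations states "This is a pilot study and we plan to recruit 40 subjects for each study group", attrition of at most 15%, and an "Exact Test for Binomial proportion with alpha=0.05". Evaluable N = 80 × 0.85 = 68. (Selection of Patients says 150; 80 is used because it reproduces the table.) Discordant n = 68 × P_tp, rounded: 61, 54, 48, 41, 34. The critical value r is the smallest with P(X ≥ r | n, 0.5) ≤ 0.025, and power = P(X ≥ r | n, p). For n = 61, r = 39. At p = 0.7 the row is 87.9, 83.7, 74.9, 66.5 and 55.4%, as printed. All other cells agree within 0.1 point. The table is not in dispute; it fixes the test and the N used below.

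**2. What an unlogged fraction does to the endpoint.** Let a be true adherence, u the fraction of injections not logged, and c the cut-off. If unlogged injections count as omissions, expected logged adherence is a(1 − u), so a patient is expected to reach good adherence only if a ≥ c/(1 − u):

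| u | c = 80% | c = 90% |
|---|---|---|
| 2% | 0.80/0.98 = 81.6% | 0.90/0.98 = 91.8% |
| 5% | 0.80/0.95 = 84.2% | 0.90/0.95 = 94.7% |
| 8% | 0.80/0.92 = 87.0% | 0.90/0.92 = 97.8% |

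Patients between two rows tend to be discordant, and all in one direction. A 3-point gap is small: 84 × 0.03 = 2.5 injections in 12 weeks.

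**3. False wins with no true effect.** The following are assumptions, not figures from the documents: true adherence logit-normal with median 90%, SD 1.0 between patients and 0.5 within patients, the same in both conditions; 84 daily doses per period (12 weeks); cut-offs of 80% and 90%; the unlogged rates shown. The test is exact McNemar, two-sided 0.05, N = 68, counting only significant results in favour of feedback (nominal 2.5%). Values differ by a point or so between simulation runs of 3,000 or more trials.

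| Unlogged, feedback v no feedback | 80% cut-off | 90% cut-off |
|---|---|---|
| Equal rates | about 1% to 2% | about 1% to 2% |
| 2% v 3% | about 3% | 6% to 7% |
| 2% v 5% | 12% to 14% | 51% to 53% |
| 2% v 8% | about 60% | about 99% |

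By symmetry, swapping the two rates gives the same false wins to the comparator and essentially none to feedback.

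**4. Other adherence models.**
- Beta-distributed omissions with mean 10% per day: at 2% v 5%, false wins are 13% (80% cut-off) and 66% (90% cut-off). At the 90% cut-off, 56.2% of patients are classed as good with feedback and 42.5% without; 20.5% are discordant, and 83.4% of those favour feedback although the true value is 50%. Equal rates give 0.4% to 1.3%. At 10% with feedback v 5% without, the comparator falsely wins in 70% and 99%.
- The figure in Insulin Non-Adherence (about one-third of patients report an average of three episodes in a month, 3/30 = 10%), with the remaining patients assumed near 99% adherent: 2% v 5% gives 4.5% and 46%; 2% v 8% gives 26% and 100%.

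**The case against.** The strongest reply is that the plan contains no wrong rule, only a missing one, and that several safeguards limit the problem. There is a one-week run-in with screen failure for improper use. Device instruction is repeated at the interim and crossover visits. Data are retrieved at each clinic visit in both conditions, so staff could see gaps. Telephone contact is at two-week intervals. These make a large difference between conditions less likely. But the run-in precedes randomization and cannot show behaviour over months with or without alerts, and no safeguard says how a blank day is coded.

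Three further objections stand and limit the point:
- A reader might infer that Assessment of Results defines every unlogged dose as an irregularity. It does not. That is the likely default where the device is the only source and no rule exists.
- A reader might infer that a lost phone connection means a lost dose record. The documents say that patients are trained to charge and connect the device, but also that it has its own memory and large storage. They do not say whether an uncharged or unconnected device would still trigger a reminder.
- The rates and cut-offs are assumed, and the result depends heavily on the cut-off, which the plan leaves undefined. At a one-point difference the distortion is modest.

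**Conclusion.** The point holds as a conditional risk. Followed as written, the plan cannot tell a missed injection from a missed log, and only one condition tells patients about gaps. If unlogged injections are more frequent without alerts, the primary comparison is biased toward feedback. Under the assumptions above, false wins rise from about 1% to 2% with equal rates to about 3% or 7% (80% or 90% cut-off) at 2% v 3%, about 12% or 53% at 2% v 5%, and about 60% or 99% at 2% v 8%.

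It would go too far to say that the primary result is biased toward feedback. The documents give no unlogged rate for either condition. The direction is plausible but not established: equal rates give no bias, and reversed rates favour the comparator. Because neither size nor direction is known, the trial needs to record the rate by condition. The plan should make this change, because the second record of doses is already being collected and is not used for this purpose.

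**What to change.** Before any outcome data are seen, add the following to Assessment of Results and Analysis of Primary Endpoint:

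- Define an omission, and code a day with no device record but a dose in the diary as not logged, not as an omission. State whether such days stay in the denominator, and how mistiming is handled on them.
- Report the number of not-logged days per patient by condition.
- Present the primary comparison twice: device-only, and device-plus-diary under the rule above. If the two disagree, say so when interpreting the superiority claim.
- Use device status or remaining pen volume to settle blank days only if the device is confirmed to store them. The documents do not show that it logs attachment or connection, or that it detects doses given while detached.

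The cost is one coding rule, one descriptive table and one sensitivity analysis, using diaries the plan already collects; their dose entries have to be put into analysable form. The downside is that diaries are self-reported by patients who know whether they receive alerts, and may over-report doses. Neither version is therefore error-free, and both should be shown.

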# Visit 14 (End of Study)

- Diabetes Treatment Satisfaction Questionnaire Status (DTSQs)
- Blood sampling for HbA1c assessment to determine efficacy of treatment
- Study diaries collected and reviewed for BG levels, episodes of hypoglycemia, insulin self-administration

During each visit, participants will have their insulin dose titrated to achieve a fasting glucose <130 mg/dL as detailed in the glargine titration algorithm. Once the fasting glucose 3-day average is <130 mg/dL, insulin doses will be kept constant, unless the participant experiences recurrent hypoglycemia or severe hyperglycemia.

**Insulin Glargine Titration Schedule.** Make adjustment every 3 days after the subject has been on insulin U100 as follows:

Mean 3 day consecutive Fasting SMBG	Glargine U100 Dose Adjustment	
>180 mg/dL	Increase glargine dose by 4 IU	
$130 - \le 180 \text{ mg/dL}$	Increase glargine dose by 2 IU	
$71 - \le 130 \text{ mg/dL}$	No change	
$\leq 70 \text{ mg/dL}$	Decrease insulin glargine dose by 10%	
$\leq$ 40 mg/dL	Decrease insulin glargine dose by 20-30%	

Upward titration should be stopped for one week after a case of hypoglycemia confirmed by a SMBG reading < 70 mg/dL unless there is an adequate explanation (e.g. omission of a meal) for the event. The study staff should instruct the subject to contact the site for any questions on the insulin dose adjustments.

Treatment satisfaction will be assessed with the Diabetes Treatment Satisfaction Questionnaire Status (DTSQs)  to be administered at baseline (week 0) and at weeks 12 and 24 to assess relative changes in the DTSQ between interventions. The amplitude of the score on the DTSQc gives the degree of change in satisfaction while the direction (positive or negative) will provide guidance on the preference of one device over the other.

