### **Selection of Patients**

**Number of subjects planned.** The total number of patients with T2D to be included in this pilot study is 150. We anticipate a dropout rate of 10% - 20% through week 24 so that each arm will have 32 subjects at week 32.

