### Analysis of Secondary Endpoints:

Secondary endpoints in this study include patient satisfaction (assessed by subjects' responses to questions 1, 7 and 8 of the DTSQc), quality of life score, insulin dose, rate of hypoglycemia, number of episodes of severe hyperglycemia and hypoglycemia. For a continuous secondary outcome (e.g. quality of life score), our analysis will be focused on determining whether the outcome difference between period after crossover (i.e. period 2) versus the period before crossover (i.e. period 1) in the Insulclock group is similar to that in the conventional device group. We will perform the analysis based on paired t-tests. Linear mixed models will be conducted to assess the study group difference while accounting for potential confounders. Appropriate transformations may be applied to determine the final linear models. For binary secondary outcomes, we will follow the analysis plan proposed for the primary endpoint.

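### The satisfaction contrast (Aim 2) exists only for patients who complete both periods, so dropout linked to feedback or alerts could bias it in either direction; a questionnaire at withdrawal would narrow the gap

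*Combined protocol and SAP*

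**What the plan says.** All references are to the combined protocol and SAP.

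- **Timing.** Assessment of Results states that the DTSQs "form will be administered at weeks 0, 12 and 24". The visit lists agree: it appears in the preparation for Visit 2, at the crossover visit and at Visit 14, and nowhere else.
- **Measures.** For satisfaction, "subjects' responses to questions 1, 7 and 8 of the DTSQc will be used". The same paragraph adds "A comparison of the score on the DTSQs from week 12 to week 24". Although the DTSQc is the named measure, no visit list includes it.
- **Analysis.** For continuous secondary outcomes, Analysis of Secondary Endpoints says "We will perform the analysis based on paired t-tests". It also plans linear mixed models, with adjustment for confounders as their stated purpose; missing scores are not mentioned.
- **Dropout.** Selection of Patients says "We anticipate a dropout rate of 10% - 20% through week 24"; Power Considerations says "We assume no more than 15% attrition rate".
- **Conditions.** Under Methods, everyone wears the Insulclock throughout. The two conditions differ only in whether the patient receives feedback and alerts.
- **Withdrawal.** The available text has no early-termination visit, no questionnaire at withdrawal and no recording of why a patient left. The week 28 contact (Duration of study) is for safety.

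**The concern.** For most outcomes, dropout is a nuisance whose link to the outcome is indirect. For satisfaction the link can be direct: a patient may leave because of how they feel about the condition they are in. Aim 2 hypothesises better satisfaction with Insulclock, and the contrast that tests it would come entirely from patients content enough with both conditions to finish. If those who left would have rated feedback differently from those who stayed, the completer mean does not describe the randomized group. A score that was never collected cannot be recovered at analysis, so this has to be settled in the visit schedule as well as in the analysis section.

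**Working it through.** **Step 1. The plan's own figure.** Power Considerations claims over 80% power for a difference of 0.41 SD, using a paired t-test at alpha 0.05 with within-patient correlation 0.3. It states "we plan to recruit 40 subjects for each study group", so N = 80, and 80 × (1 − 0.15) = 68 pairs.

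- SD of a within-patient difference = SD × √(2 × (1 − 0.3)) = 1.183 SD.
- Noncentrality = (0.41 / 1.183) × √68 = 2.86.
- Two-sided power (noncentral t, 67 df) = 80.4%.

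The stated figure reproduces, and it counts complete pairs only. From 80 recruited, 10% dropout leaves 72 pairs (82.6%) and 20% leaves 64 pairs (77.9%), slightly below the stated level.

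**Step 2. Who has which score.**

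| Patient | Week 0 DTSQs | Week 12 DTSQs | Week 24 DTSQs | DTSQc across the crossover | In paired test |
|---|---|---|---|---|---|
| Completer | yes | yes | yes | yes, if given | yes |
| Leaves in period 2 | yes | yes | no | no | no |
| Leaves in period 1 | yes | no | no | not possible | no |

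The week 0 score precedes the assigned condition. A period 1 leaver therefore has no on-treatment score, and a period 2 leaver has one for the first condition only.

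**Step 3. How many.** Selection of Patients plans 150 patients, but Power Considerations and Study Schedule both give 80. At 10% to 20% dropout:

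- N = 80: 8 to 16 leavers.
- N = 150: 15 to 30 leavers.

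The 32 per arm expected in Selection of Patients equals 40 × 0.8, so it fits N = 80. The conflict needs resolving in its own right.

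**Step 4. Possible size of the bias.** Let f be the dropout share, s the share of leavers whose exit is linked to alerts, and D how far (in outcome SD) their feedback-minus-no-feedback difference lies below that of everyone else. Other leavers are taken to resemble completers. Then

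completer mean − mean in all randomized = f × s × D.

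Only f comes from the documents. Assuming s = 25% to 100% and D = 0.5 to 1.5 SD:

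| f | Smallest | Largest |
|---|---|---|
| 10% | 0.10 × 0.25 × 0.5 = 0.01 SD | 0.10 × 1 × 1.5 = 0.15 SD |
| 15% | 0.15 × 0.25 × 0.5 = 0.02 SD | 0.15 × 1 × 1.5 = 0.23 SD |
| 20% | 0.20 × 0.25 × 0.5 = 0.03 SD | 0.20 × 1 × 1.5 = 0.30 SD |

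The sign follows D. If the linked exits come from patients unhappy without feedback, D is negative and bias of the same size runs against feedback. If s or D is zero, there is no bias.

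**Step 5. What would erase an effect.** If completers show 0.41 SD, the overall mean is zero when leavers average −0.41 × (1 − f) / f: −3.69 SD at 10% dropout, −2.32 SD at 15% and −1.64 SD at 20%. Dropout at the planned level could distort the estimate, but cancelling a full design effect would need extreme scores among leavers.

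**The case against.** The strongest case against has five parts.

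- **Direction.** A reader might infer that the result must be tilted in favour of Insulclock. The documents give no dropout by condition or reason. On the DTSQc scale of −3 to +3, suppose completers average +1. Leavers at 0 to −3 imply an overstatement of 0.10 × (1 − 0) = 0.1 to 0.20 × (1 + 3) = 0.8 points, but leavers at +2 to +3 imply an understatement of 0.10 × (2 − 1) = 0.1 to 0.20 × (3 − 1) = 0.4. Each range gives every leaver a score on the same side, so neither is an estimate. This objection stands in full.
- **The device.** Annoyance with the device need not favour either condition, because it is worn in both. A week of use precedes randomization, and patients who cannot use it properly are screened out, which may remove some poor-fit users. This stands: only exits tied to feedback or alerts act directly on the contrast.
- **Leavers without any score.** That would overstate the gap. Period 2 leavers keep week 0 and week 12 scores, and the planned mixed model could use them. This stands, although the model would infer the missing second-condition score from patients who stayed, which is unsafe if that condition caused the exit.
- **Detection.** It would be wrong to say that no planned analysis could show a warning sign. The opening paragraph of Statistical Analysis compares the share of patients who stay on therapy, which could reveal unequal discontinuation. It would not show why patients left or how satisfied they were.
- **Importance.** This is a secondary outcome of a pilot, and the primary McNemar comparison also needs both periods. That limits the weight of the point. Satisfaction still merits its own remedy because the cause of leaving can be the outcome itself and because a score can be obtained at exit.

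**Conclusion.** The point holds as a risk of informative dropout of unknown direction. It is established that the between-condition satisfaction score is confined to patients who complete both periods, that 10% to 20% are expected not to, and that neither a score nor a reason is collected when they leave. The size cannot be derived from the documents: about 0.01 to 0.30 SD in either direction on assumed inputs, so from trivial to a large part of the 0.41 SD design difference, and zero if leaving is unrelated to satisfaction. This reading assumes that the satisfaction scores are analysed as continuous outcomes with the paired t-test. The documents do not support a claim that the Aim 2 result will favour Insulclock, or that every leaver lacks usable data. The change is a worthwhile, inexpensive improvement to a named aim; it does not touch the primary endpoint.

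**What to change.** 1. **Collection** (crossover visit, Visit 14 and Assessment of Results). Have a patient who leaves early complete the DTSQs at the last contact, by telephone if needed, rating the condition in use. Give the DTSQc as well only if the patient has already crossed over; a period 1 leaver cannot answer it. Record the condition at exit and the reason for leaving.
2. **Analysis** (Analysis of Secondary Endpoints). Make the linear mixed model already planned, with condition and period as fixed effects and patient as a random effect, the main DTSQs analysis in place of the paired t-test. Use all available on-treatment DTSQs scores, including those taken at withdrawal. Keep the DTSQc as a measure among patients who crossed over, and say so.
3. **Sensitivity analysis (optional).** Vary the values assumed for leavers without a score, in both directions.

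While editing, add the DTSQc to the visit lists.

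**Cost.** One short questionnaire per leaver, which can fit the existing two-weekly telephone contacts, plus a few sentences of analysis text. Some leavers will decline, and a withdrawal score reflects shorter exposure than a scheduled one, so the gap shrinks but does not close.
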